1 CLINICAL PROTOCOL SUMMARY

Title	ECAP Study: A prospective, multicenter, single-arm study examining ECAP-controlled, closed-loop stimulation with the Evoke Spinal Cord Stimulator (SCS) System to treat patients with chronic pain of the trunk and/or limbs.
Investigational Device	Evoke Spinal Cord Stimulator (SCS) System (Evoke System) The Evoke System measures and records spinal cord (SC) activation resulting from stimulation via evoked compound action potentials (ECAPs). The Evoke System can be programmed to provide ECAP-controlled, closed-loop SCS or open-loop, fixed-output SCS; ECAPs may be measured and recorded in either stimulation mode.
Target Indication for Use	The Evoke System is indicated as an aid in the management of chronic, intractable pain of the trunk and/or limbs, including unilateral or bilateral pain associated with the following: failed back surgery syndrome, intractable low back pain and leg pain.
Purpose	The purpose of this study is to evaluate neurophysiological measures and clinical outcomes of the Evoke System to treat trunk and/or limb pain in a real-world population.
Study Design	This study is a prospective, multicenter, single-arm study. Data will be collected at baseline, time of procedure (trial and permanent), trial phase, and at 1, 3, 6, 12, 18, and 24 months post-implantation.
Primary Objective	The primary objective of this study is to collect data in a real-world population while further characterizing neurophysiological measures and clinical outcomes.
Statistical Analysis	A number of outcome variables of interest will be collected and assessed across study visits. No pre-planned formal statistical hypothesis tests will be performed. Multivariable regression modeling and descriptive statistics will be utilized.
Data Collection	The following data will be collected: 
 • Baseline characteristics and demographics • Procedure characteristics • Medications • Study Pain Assessment • PROMIS-29+2 • PROMIS-10 Global • Profile of Mood States (POMS 2-A Short) • Patient Global Impression of Change (PGIC) and Patient Satisfaction • Stimulation characteristics • Posture change measurements • Neurophysiological measurements • Programming parameters and characteristics • Safety (adverse events, device deficiencies, protocol deviations)
Inclusion Criteria	Subjects enrolled in this study must meet all of the following inclusion criteria (based on investigator judgement): 
 1. Subject has chronic intractable pain of the trunk and/or limbs (VAS ≥ 6 cm in at least one of the regions intended to be treated with SCS). 2. Subject is willing and capable of giving informed consent and able to comply with study-related requirements, procedures, and visits. 3. Subject has trunk and/or limb pain such that lead placement will be in the lumbar to cervical region.
Exclusion Criteria	Subjects enrolled in this study must not meet any of the following exclusion criteria (based on investigator judgement): 
 1. Subject is unable to operate the system. 2. Subject is an unsuitable surgical candidate. 3. Subject has a condition currently requiring or likely to require the use of diathermy. 4. Subject has another implantable stimulator such as demand type pacemakers or cardioverter defibrillator. 5. Subject is <18 years old. 6. Subject is pregnant or nursing.

	
 7. Subject is allergic, or has shown hypersensitivity, to any materials of the neurostimulation system which come in contact with the body. 8. Subject is involved in an injury claim under current litigation or has pending/approved worker's compensation claim. 9. Subject has prior experience with SCS. 10. Subject is being treated with electroconvulsive therapy (ECT) or transcranial magnetic stimulation (rTMS).
Investigation Sites	Up to 25 US sites.
Enrollment	Up to 300 subjects (enrollment defined as trial procedure). Enrollment is anticipated to take 36 months.

2 BACKGROUND (REPORT OF PRIOR INVESTIGATIONS)

2.1 Disease Summary

Chronic pain is one of the most common reasons for medical care resulting in one of the largest and costliest medical health problems in the developed world and it is likely to worsen(1–3). Chronic pain persists well after the initial injury or illness that produced the initial pain has healed. The International Association for the Study of Pain (IASP) has defined chronic pain as pain that lasts more than three to six months beyond the normal time of healing(4). Chronic pain invariably is generated by physical, psychological, and environmental factors (bio-psycho-social concept of chronic pain). It is difficult to manage, and many afflicted patients have a florid medical history with multiple comorbidities. Chronic pain is also difficult to generally define beyond its chronicity. Chronic pain is routinely characterized by multiple aspects including: the nature of the pain as perceived and reported (e.g. nociceptive, neuropathic, ischemic), the pathophysiology causing the pain (e.g., painful diabetic neuropathy), or the anatomical location that the pain is perceived (e.g., chronic low back pain), or a combination of these (e.g., discogenic low back pain). The published *Classification of Chronic Pain, Descriptions of Chronic Pain Syndromes and Definitions of Pain Terms* from IASP lists around 100 separately identifiable chronic pain conditions(4).

2.2 Current Treatment Options

The multifaceted nature of chronic pain requires interdisciplinary assessment and multimodal treatment. First line treatment strategies are generally conservative treatments including: exercise programs, physical therapy (PT), occupational therapy, cognitive behavioral therapy (CBT), biofeedback, acupuncture, transcutaneous electrical nerve stimulation (TENS), and oral medications. Second line treatments become more intensive and involve the use of more extreme CBT, more powerful medications such as systemic opioids, and interventional techniques such as nerve blocks (local anesthetic or steroids) and spinal injections. The last line of treatment involves more advanced therapies that require surgical interventions. Systems such as intrathecal drug delivery (IDD) or spinal cord stimulators (SCS) may be implanted. Surgery to repair an anatomical issue responsible for the pain may be performed. Finally, surgical techniques that block pathways to the brain such as cordotomy, rhizotomy, and thalamotomy may be used rarely in extreme cases.

Recent guidelines and the literature on the treatment for chronic pain of the trunk and/or limbs demonstrate that each of the surgical interventions have the potential to be effective in managing pain, increasing patient activity, and to result in high patient satisfaction when conservative treatment modalities have failed. The risk profile for SCS therapy has advantages compared to surgical revision and neuroablation due to the fact it is reversible as the device can be surgically removed. Furthermore, typically patients undergo a trial period with SCS, in which leads are temporarily placed in the epidural space and connected to an external pulse generator, to assess tolerability and the degree of pain relief prior to being permanently implanted. The Neuromodulation Foundation recommends that an SCS trial precede major reconstructive procedures and ablative therapies (5). In addition, SCS therapy has the

advantage of not having drug side effects, including respiratory distress, as compared to IDD systems, or addictive properties, as compared to opioid usage, which is currently of epidemic proportions in the United States (US). There is consensus among national medical societies to recommend SCS as a treatment option in patients with chronic, severe pain for which conservative treatment modalities have failed or are contraindicated(5–13). SCS may be delivered in parallel with other therapies and should be used as part of an overall multimodal treatment strategy.

2.3 Rationale for the Proposed Treatment

SCS is a well-established therapy with a long history of use in treating chronic intractable pain of the trunk and/or limbs. SCS consists of applying an electrical stimulus to the spinal cord which causes the activated fibers (e.g., A β -fibers) to generate action potentials. A β -fibers are the low-threshold sensory fibers in the dorsal column that contribute to inhibition of pain signals in the dorsal horn (14). The action potentials summed together form the electrically evoked compound action potential (ECAP). Therefore, ECAPs are a direct measure of spinal cord fiber activation that generates pain inhibition for an individual.

The original SCS device consisted of an implanted radiofrequency-controlled power source connected to two electrodes (Shealy et al. 1967). Over the last 50 years there have been many advances in SCS therapy, including a better understanding of the target patient population and improvements in device technology and reliability. The technology has evolved from large profile, single channel, non-rechargeable implantable pulse generators (IPG) and monopolar leads, to smaller profile, multichannel, rechargeable IPGs with new programming parameters and multiple contact leads with various electrode arrays.

A significant challenge that still remains in SCS, however, is the ever-changing distance between the stimulating electrodes relative to their spinal cord target. The electrode is fixed in the epidural space, while the spinal cord changes position within the cerebrospinal fluid with every movement, including the cardiorespiratory cycle (e.g., breathing, heartbeat), coughing, or changes in body position (e.g., standing, sitting, lying). Small changes in distance between the electrode and spinal cord result in large changes in the current reaching the spinal cord, as the current density with SCS varies with the inverse of the distance between the electrode and spinal cord squared (15). Thus, at a fixed SCS output level, the degree of spinal cord (SC) activation varies widely.

Currently available SCS systems, regardless of the stimulation parameters, are open-loop systems and incapable of measuring SC activation or varying stimulation output based upon such measurement. For these systems, the stimulation is fixed based on in-clinic programmed settings. There is a feed-forward system (16) with an accelerometer located in the pulse generator, distant from the electrode to spinal cord interface, that utilizes pre-programmed, fixed output stimulation programs based on gross postural changes (17). In all cases, however, the stimulation output does not vary based upon how much current is reaching the spinal cord, which can result in significant variation in SC activation. To manage variance in stimulation, patients generally reduce the stimulation amplitude using a remote control, which improves tolerability of stimulation and reduces the incidence of overstimulation, but also reduces the amount of analgesia that can be achieved (18).

To address these limitations, the Evoke System has been developed that is able to record *in vivo* human spinal cord electrophysiology continuously in real time (19,20). An ECAP is measured for each stimulation pulse delivered; this reflects the degree of SC activation elicited by SCS. The system may operate in fixed-output, open-loop (plus ECAP measurement) or ECAP-controlled, closed-loop mode. In open-loop SCS, the system measures ECAPs, which may be used to determine optimal stimulation settings, but are not used to automatically adjust stimulation current to maintain a target response. In closed-loop SCS, the difference between the measured ECAP and the target ECAP amplitude is minimized by automatically adjusting the stimulation current to maintain consistent SC activation within the individuals' therapeutic window. By real-time modulation of the output current, the closed-loop system

maintains consistent SC activation with corresponding inhibition of pain processing pathways, and thus maximizes the therapeutic effect.

The Evoke System has been designed to ensure that there are no additional risks to patients compared to other commercially available SCS systems, which have a long history of safety and effectiveness. The Evoke System is the same or functionally similar to other SCS devices already on the market in terms of intended use, and with respect to their biological and technical characteristics with the primary difference being that it measures and records ECAPs, and in addition to open-loop stimulation (equivalent to other commercially available SCS systems), it offers closed-loop stimulation using ECAPs as the feedback mechanism. Importantly, the Evoke System stimulation parameters associated with patient safety and actual product use for both stimulation modes (i.e., open- and closed-loop) fall within the range of currently approved SCS systems.

[figure not shown]
[figure not shown]
2.4 Summary of Prior Preclinical and Clinical Experience

[figure not shown]
[figure not shown]
Figure 1 is a bar chart showing the mean number of days to first symptom onset for different age groups. The y-axis is labeled 'Age group' and the x-axis is labeled 'Mean days to first symptom onset'. The chart shows that older age groups generally have a higher mean number of days to first symptom onset. The data is as follows:

[figure not shown]
Age group	Mean days to first symptom onset
0-19	3.0
20-29	3.5
30-39	4.0
40-49	4.5
50-59	5.0
60-69	5.5
70-79	6.0
80-89	6.5
90+ years	7.0

[figure not shown]
© 2019 Pearson Education, Inc.

the first time in the history of the world, the people of the United States have been called upon to determine whether they will submit to the law of force, or the law of the Constitution. We have said to the world, we will not submit.

2.5 Rationale for Clinical Study

The clinical experience with the Evoke System to date suggests that the device performs as intended and is safe and effective. Additionally, the unique ability of the Evoke System to measure neurophysiological data and operate in closed-loop mode has the potential to advance the science of pain management. This study has been developed to further understand the clinical utility of the neurophysiological measurements that the Evoke System is capable of measuring, as well as provide ongoing evidence in support of safety of the device. In alignment with IMMPACT recommendations (24), data collected in this study will be used to interrogate and analyze the underlying neurophysiological mechanisms of chronic pain with the goal of furthering a mechanism-based treatment approach to improve the efficacy of neuromodulation therapies.

3 DEVICE DESCRIPTION AND INDICATION FOR USE

3.1 Device Description

3.1.1 Investigational Device

The Investigational device is the Evoke Spinal Cord Stimulator (SCS) System. It consists of a stimulator (implantable and external), leads, programming system, accessories, and surgical tools. Please refer to the current Instructions for Use (IFU) for the most up-to-date description of the System and Accessory Components.

The Evoke System can measure ECAPs following every stimulation pulse, and can use ECAPs in a feedback mechanism to deliver closed-loop stimulation. The Evoke System records ECAPs following every stimulation pulse from two electrodes not involved in stimulation. The recorded ECAP signal is sampled by the stimulator and processed to allow measurement of the ECAP amplitude. The feedback mechanism minimizes the difference between the measured ECAP amplitude and the ECAP amplitude target (set by the clinician and adjusted by the patient using the pocket console) by automatically

adjusting the stimulation current for every stimulus. In doing so, it maintains spinal cord activation near the target level (Figure 1). The system is designed to operate in either ECAP-controlled, closed-loop stimulation mode, or open-loop (fixed-output) stimulation mode equivalent to other commercially available SCS systems. ECAPs may be measured and recorded in either stimulation mode.

[figure not shown]

Figure 1: Feedback Mechanism – ECAP-Controlled, Closed-Loop SCS

3.2 Target Indication for Use

The Evoke System is indicated as an aid in the management of chronic intractable pain of the trunk and/or limbs, including unilateral or bilateral pain associated with the following: failed back surgery syndrome, intractable low back pain and leg pain.

4 STUDY PURPOSE AND OBJECTIVES

4.1 Study Purpose

The purpose of this study is to evaluate neurophysiological measures and clinical outcomes of the Evoke System to treat trunk and/or limb pain in a real-world population.

4.2 Primary Objectives

The primary objective of this study is to collect data in a real-world population while further characterizing neurophysiological measures and clinical outcomes.

5 STUDY DESIGN

This study is a prospective, multicenter, single-arm study designed to examine ECAP-controlled, closed-loop stimulation with the Evoke System to treat patients with chronic pain of the trunk and/or limbs.

Subjects with chronic, intractable pain of the trunk and/or limbs will be screened for participation in this study. Subjects who provide informed consent and meet the study eligibility criteria undergo a trial procedure and will be enrolled. Following the trial phase subjects may receive a permanent implant and be followed up at 1-, 3-, 6-, 12-, 18-, and 24-months following the permanent implant.

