⁵ Initial programming will follow the trial procedure and following the permanent implant procedure (prior to the day of the 1-month follow-up visit); it need not occur on the procedure date. Reprogramming may occur as needed for optimization throughout the study.

⁶ Additional optional assessments may be requested any time during the study that subjects can elect to participate in.

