8.5 Implant Procedure/Post-procedure

Subjects will be approved to undergo implantation of the Evoke System if the subjects' trial was successful based on physician and subject determination.

The permanent implant will involve the implantation of the Evoke stimulator and one or two Evoke leads. The implant procedure will be performed in accordance with standard of care and the IFU, and programming will be performed in accordance with the IFU. Timing of post-procedure programming will occur at the discretion of the Investigator, prior to the 1-month follow-up visit.

The following data will be collected during the implant procedure/post-procedure:

- Implant procedure data
- X-rays (AP and lateral) during the procedure
- X-rays (AP and lateral) post-procedure, prior to 1-month follow-up
- Neurophysiological measurements (optional)
- Device programming

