8.6 Follow-up Visits

Subjects will be followed-up at 1 month (30, -14 days, +21 days), 3 months (90±21 days), 6 months (180±30 days), 12 months (365±60 days), 18 months (545±90 days), 24 months (730±90 days). Subjects may have their device reprogrammed throughout follow-up. The following data will be collected during follow-up:

- Study Pain Assessment
- PROMIS-29+2
- PROMIS-10 Global
- POMS 2-A Short
PGIC & Patient Satisfaction
- Stimulation characteristics
- Posture change measurements
- Neurophysiologic measurements
- Device programming (as needed)

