11.2 Study Outcomes

A number of outcome variables of interest will be collected and assessed across study visits to characterize neurophysiological measures and clinical outcomes with the Evoke System.

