12.3 Potential Benefits

There are several potential benefits of the Evoke System, and specifically with regard to ECAP-controlled closed-loop stimulation, to participating study subjects suffering from chronic, intractable pain of the trunk and/or limbs. These include:

- The Evoke System may provide insight into the neurophysiological mechanisms of chronic pain and SCS.
- The Evoke System may provide significant pain relief.
- The Evoke System may allow patients to reduce their pain medications.
- The Evoke System may improve patients' quality of life, sleep quality, emotional and/or physical functioning.
- The Evoke closed-loop stimulation mode may reduce variation in electrical field strengths reaching the spinal cord due to normal physiological activity and movement.
- The Evoke closed-loop stimulation mode may be more effective in providing pain relief compared to open-loop stimulation.

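### Must the plan say how stimulation mode and days since programming enter the results, given that its title names closed-loop stimulation?

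*Combined protocol and SAP*

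**What the plan says.** **Scope.** The title in the protocol summary (Section 1) and Section 5 name the closed-loop mode. Section 5 calls the study "designed to examine ECAP-controlled, closed-loop stimulation with the Evoke System to treat patients with chronic pain of the trunk and/or limbs". Section 4.1 gives the purpose as to "evaluate neurophysiological measures and clinical outcomes of the Evoke System to treat trunk and/or limb pain in a real-world population". Section 11.2 says outcomes are collected "to characterize neurophysiological measures and clinical outcomes with the Evoke System". Section 4.2 names neither the device nor a mode. Section 1 describes the device: "The Evoke System can be programmed to provide ECAP-controlled, closed-loop SCS or open-loop, fixed-output SCS". Section 12.3 lists as a possible benefit that "The Evoke closed-loop stimulation mode may be more effective in providing pain relief compared to open-loop stimulation".

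**Programming.** Sections 8.4, 8.5 and 8.7 refer programming to the instructions for use (IFU), which are not among the documents. Section 8.7 allows reprogramming as often as needed. The protocol itself does not fix the mode during follow-up. For the permanent implant, Section 8.5 says: "Timing of post-procedure programming will occur at the discretion of the Investigator, prior to the 1-month follow-up visit". Footnote 5 to Table 4 in Section 8.1 agrees, placing first programming "prior to the day of the 1-month follow-up visit); it need not occur on the procedure date".

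**Visits.** Implant is Day 0 in Table 4. Section 8.6 says: "Subjects will be followed-up at 1 month (30, -14 days, +21 days), 3 months (90±21 days), 6 months (180±30 days", and continues to 12, 18 and 24 months.

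**Analysis.** Section 11.3 plans summary statistics and no formal hypothesis test. It allows exploratory regression, repeated-measures and GEE analyses without naming covariates. Sections 11.1 to 11.4 do not mention mode or time since programming.

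**The concern.** Two points looked wrong.

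The first is attribution. If some subjects receive open-loop stimulation as their ongoing therapy, a summary of all subjects describes the system in mixed use. A reader who starts from the title would take it as a closed-loop result. The sponsor itself says the modes may differ in pain relief, so the distinction could matter. A single arm gives no internal comparison that would show which mode a result belongs to.

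The second is the time origin. Visit labels count from implant, but therapy from the implant starts when the device is programmed. If that date varies widely, the 1-month results mix subjects who have only just started with subjects who have had weeks of stimulation. Part of an apparent trend from 1 to 3 months could then come from when devices were programmed and not from the course of the effect.

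At stake would be how the clinical outcomes are labelled and how the early visits are read. Type I error and power are not involved, because no formal test is planned.

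**Working it through.** **The plan's own figure.** Section 11.1 states a half-width of about 6 percentage points or less for a two-sided 95% exact binomial interval with N = 300 and incidence 50%. With 150 events in 300, the Clopper-Pearson interval is 44.2% to 55.8%. The half-width is (55.8 − 44.2)/2 = 5.8 points, so the figure reproduces. It concerns all 300 subjects and does not depend on mode. For illustration only, since the documents give no share in closed-loop mode: if 90%, 80%, 70% or 50% of 300 subjects were in that mode, a closed-loop-only estimate at 50% would have a half-width of 6.12 (n = 270), 6.50 (n = 240), 6.96 (n = 210) or 8.26 (n = 150) points.

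**Days since first programming of the implant.** Inputs are the windows in Section 8.6 and the programming limit in Section 8.5 and Table 4, footnote 5. Let P be the day of first programming and V the visit day, both counted from implant.

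- The 1-month visit falls between day 30 − 14 = 16 and day 30 + 21 = 51.
- P runs from 0 to one day before the 1-month visit, so its latest value is 51 − 1 = 50.
- The maximum of V − P is the upper window limit, with P = 0.
- The minimum is 1 at the 1-month visit. At later visits it is the lower window limit minus 50.

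| Visit | Window (days from implant) | Days since first programming | Max/min | Max/min from the window alone |
|---|---|---|---|---|
| 1 month | 16–51 | 1–51 | 51 | 3.2 |
| 3 months | 69–111 | 69 − 50 = 19 to 111 | 5.8 | 1.6 |
| 6 months | 150–210 | 150 − 50 = 100 to 210 | 2.1 | 1.4 |
| 12 months | 305–425 | 305 − 50 = 255 to 425 | 1.7 | 1.4 |
| 18 months | 455–635 | 455 − 50 = 405 to 635 | 1.6 | 1.4 |
| 24 months | 640–820 | 640 − 50 = 590 to 820 | 1.4 | 1.3 |

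The 1-month and 3-month visit windows do not overlap, but the permitted times since programming do, from 19 to 51 days.

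**What the overlap means.** It is an overlap between different subjects. In one subject, with visits V1 and V3, the added time since programming is (V3 − P) − (V1 − P) = V3 − V1. P cancels. The gap runs from 69 − 51 = 18 to 111 − 16 = 95 days, whatever the programming date, so every subject has more stimulation time at 3 months than at 1 month. The ratio of 51 comes from a denominator of one day. The 19-day minimum needs three extremes in one subject: programming on day 50, the 1-month visit on day 51 and the 3-month visit on day 69. Section 8.4 adds that implanted subjects had a stimulation trial first, so programming the implant is not their first exposure.

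**The scope statements side by side.** Section 5 says closed-loop stimulation delivered with the Evoke System. Sections 4.1 and 11.2 name the same system and leave the mode out. General wording beside specific wording is not a contradiction. It would become one only if subjects were treated open-loop over the long term. The one required assessment that uses both modes is the posture test in Section 7.7, which is a measurement procedure. The optional assessments in Section 7.10 may also vary programming.

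**The case for a change.** The strongest case for a change is that the two scopes are not synonyms in this protocol. The device has two modes, Section 12.3 says one may relieve pain better, and nothing in the protocol fixes the mode during follow-up. Section 11.3 allows one-sample t-tests with nominal p-values, and Section 11.4 lets analyses be run at any time, so results could appear under a closed-loop title without any statement of mode. The remedy looks cheap: aligned wording and two descriptive rows per visit, drawn from the device logs (Section 7.9) or the programming worksheets (Section 13.8.1).

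Part of this stands. Section 11 is silent on both points, and a report that claims a closed-loop effect should say how much of the stimulation was closed-loop. The timing argument also keeps some force at 1 month: if response changes quickly after programming, subjects programmed late are seen at an earlier stage, even though P cancels from the within-subject gap.

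The rest does not carry. Open-loop therapy is a possibility that turns on an IFU the documents do not include. Labelling the main result as either mode would settle in advance a question the documents leave open, and would be wrong if use is closed-loop in practice. Making an all-implanted summary the main result would add an analysis population that Section 11 does not define. Section 7.9 gives its logged items as examples, so it shows neither that mode is recorded nor that it is missing.

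**Conclusion.** No change to the plan follows. This is missing detail that analysts can supply sensibly, and writing it in would alter no result.

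The stated purpose is to describe outcomes with the system in a real-world population. Summaries of all subjects at visits timed from implant do that validly, including whatever mix of modes and programming dates occurs in practice. Because the exploratory models name no covariates, mode and days since programming can enter them wherever the data exist. Any comparison by mode would be exploratory in any case, since subjects are not randomised to mode.

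The size is limited. Permitted time since programming is 1 to 51 days at 1 month and 19 to 111 days at 3 months. From 12 months on, the max/min ratio is 1.7 or less, against 1.4 or less from the visit windows alone. These are bounds and not expected values; the documents give no typical programming date, so no effect on an outcome can be estimated. The stated precision of about 6 points is unaffected.

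The conclusion assumes that reports are framed by the purpose in Section 4.1. It would need another look if a substantial share of follow-up proved to be open-loop therapy and the results were still presented as effects of closed-loop stimulation. That would be a fault of the report, and the plan does not require it.
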